9.2 Sample Size and Analysis Methodology

A total of 60 participants will be randomized into one of three conditions: (1) 1000 mg/day resveratrol (n = 20), (2) 1500 mg/day resveratrol (n = 20), or (3) vegetable cellulose (n = 20). Conservatively, presuming a repeated measures correlation for a participant is 0.7 (baseline explains about 50% of the variation at the post test), a study of 18 completers in each of the three groups has 80% power to detect a difference of 0.69 standard deviations in this contrast. Secondarily, we shall contrast each pair of treatments using a two-sided t-test (Satterthwaite-corrected for potentially unequal standard deviations) with 80% power, to detect a difference of 0.81 standard deviations. All comparisons will be accompanied by point and 95% confidence intervals for effect sizes.

From a parallel study, we estimate that baseline STATE 3 mitochondrial respiration (Primary Outcome) will have a mean of about 120 and a standard deviation of about 40. Hence 0.69σ (0.81 σ) represents sensitivity to better than a 25% (30%) change from baseline for STATE 3 mitochondrial respiration, respectively.

Robustness of Methods absent missing data: Based upon our experience, STATE 3 is not expected to be outlier prone, making the t-test highly robust against non-normality, even for moderate size samples such as in this trial. In clinical studies, where the comparison is between a placebo and an active treatment, comparing changes between treatments from baseline to a post-test, it is expected that the variability in the control group (pure replication) will be smaller than that in the experimental group (replication plus treatment). The Satterthwaite method deals with this contingency, whether or not it really occurs in our trial. Of course, the most important aspects of the analysis are the point estimates and 95% confidence intervals for the mean differences between the three pairs of treatments. The Satterthwaite method will be used for these as well.

Missing Data: Since the analysis is primarily based on the second biopsy, missing data represent a potential problem.

Sensitivity analysis for Baseline Imbalance: Using baseline BMI, Baseline STATE 3, and gender, but not treatment, we shall develop a prediction equation via a linear model for the final STATE 3 value. Next, we shall use the predicted value for those missing the final STATE 3 value, and conduct permutation t-tests for each pair of treatments, replacing missing values by the predicted value. The type of bias that this corrects for is that missing values by be disproportionate in the arms according to the baseline value. For example, high baseline BMI may have more missingness on one arm while low BMI has more missingness on another. While this analysis corrects for interaction between treatment and missingness for baseline covariates, it does not account for missingness that develops during the study based on treatment vs. control issues. For example, if the treatment is associated with some subjects getting a headache and this leads to withdrawal from the study, this sensitivity analysis will not cover that contingency.

Sensitivity analysis for withdrawals for patient related study events, recognizing the events may not be measurable. First, we shall try to get a follow-up biopsy on every subject, ideally at the end of month 3, whether or not the subject completes the study medication program. Second, we shall ask the subject to provide reasons for withdrawal, based on a brief questionnaire. Third, we shall compare the withdrawal rates for the three treatment groups via an exact chi-square analysis. While an approximately equal withdrawal rate is not necessarily indicative of resolution, it is a reasonable assessment to make. Finally, using repeated measures mixed models methods, we shall compare the BMI trajectories for withdrawals vs. non withdrawals, stratified for treatment as a surrogate to the question as to whether the event of withdrawal is related to how the subject is doing on the trial. The month one and month two data will be used, as that will be missing for month 3.

Secondary analyses derived from the biopsy will be analyzed as above, but the study is powered strictly around STATE 3. Analysis on secondary variables that have repeated measures will utilize linear mixed model analysis of variance with unstructured covariance for repeated measures. Sensitivity analyses will be done via t-tests, utilizing the Satterthwaite correction for changes from baseline to three months, with last observation carried forward for missing data.

Occurrence of side effects will be evaluated by Fisher's Exact test.

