9. STATISTICAL CONSIDERATIONS

9.1 General Design Issues

A parallel three arm design of placebo (A) vs. standard dose resveratrol (B) vs. high dose resveratrol (C) will be used to test the primary hypothesis that the unweighted average of the target population means B and C is the same as that of A. This will be tested at p=0.05 (two-sided) by a Satterthwaite-corrected contrast. The analysis does not require equal variances in the three target populations, nor does it require that the means for B and C are the same. As our dependent variable, we will use the difference between the post-test value (90 days) and baseline. The primary and secondary aims and hypotheses are listed below.

Specific Aim 1. To examine the effects of resveratrol treatment on mitochondrial function (State 3 and 4 respiration on permeabilized muscle fibers, COX, CS enzyme activities and mitochondrial DNA content) in muscle samples of older adults.

Hypotheses. Compared to placebo, resveratrol supplementation will increase mitochondrial respiration (State 3=primary outcome, State 4), COX, CS enzyme activities, and mitochondrial DNA content in muscle specimens from the *vastus lateralis*.

Specific Aim 2. To evaluate the effects of resveratrol supplementation on levels of PGC-1 α , AMPK, and sirtuins (SIRT1 and SIRT3) in muscle samples of older adults.

Hypotheses. Compared to placebo, resveratrol treatment will increase PGC-1α (primary outcome), AMPK, SIRT1, and SIRT3 levels in muscle specimens obtained from the *vastus lateralis*.

Exploratory Aims. Explore the effects of resveratrol supplementation on measures of physical function, metabolic risk factors, and changes in physical activity in older adults.

Hypotheses. Compared to placebo, resveratrol supplementation will (1) increase walking speed, (2) improve physical performance, (3) increase resistance to muscle fatigue, (4) reduce established metabolic risk factors (i.e. diastolic blood pressure and blood levels of insulin and glucose), and (5) increase levels of spontaneous physical activity.

The proposed study will be the first to test whether resveratrol improves muscle mitochondrial function, and the mechanisms that underlie this potential improvement in older adults. An important exploratory goal is to determine whether the hypothesized biological changes in the mitochondria

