9.3 Definition of Populations

Intent-to-treat population for the primary outcome is synonymous to those getting baseline and three-month biopsies, whether or not they adhere to the treatment. Every effort will be made to bring back participants for their three month (post-treatment) biopsy visit, regardless of their levels of adherence. Intent-to-treat for serial measurements will include those with at least one of their follow-up visits. As above, we shall make every effort to get all follow-up visits completed, regardless of adherence.

The per protocol (PP) population will consist of all patients in the ITT population who are not major protocol violators. Specifically, PP population will consist of individuals who did not take any prohibited therapies during the trial, had $\geq 90\%$ adherence with prescribed regimen based on pill counts, and completed all baseline and post-treatment assessments.

The gold standard for clinical trials is by intent-to-treat. An analysis of the prognostic significance of actual dose consumed over the active period has value since it will allow for further analysis of dose effects. This will be a secondary analysis, and will allow for determination of whether higher consumption while on active medication results in greater changes to outcome variables. For this study, a completer analysis will be performed on the target population of older adults (age \geq 65 years).

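### The missing-biopsy sensitivity analysis predicts State 3 without regard to arm, so it shrinks a real effect even when dropout is harmless, and it specifies no imputed primary contrast

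*Combined protocol and SAP*

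**What the plan says.** Section 9.1 sets the primary test on change in State 3: the null hypothesis is that "the unweighted average of the target population means B and C is the same as that of A", where A is placebo and B and C are the two resveratrol doses. Section 9.3 limits the primary intention-to-treat population to participants with both biopsies. Section 9.2 accepts that "Since the analysis is primarily based on the second biopsy, missing data represent a potential problem".

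The remedy is in the section 9.2 paragraph on sensitivity to baseline imbalance. The prediction rule is "Using baseline BMI, Baseline STATE 3, and gender, but not treatment, we shall develop a prediction equation via a linear model". The plan will then "conduct permutation t-tests for each pair of treatments, replacing missing values by the predicted value". It says that "this analysis corrects for interaction between treatment and missingness for baseline covariates", and adds that withdrawal caused by treatment is not covered.

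The next paragraph seeks a follow-up biopsy "whether or not the subject completes the study medication program", and section 9.3 adds: "Every effort will be made to bring back participants for their three month (post-treatment) biopsy visit, regardless of their levels of adherence". The remaining withdrawal steps (reasons, withdrawal rates, BMI trajectories) give no State 3 estimate. No imputed version of the primary contrast appears.

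**The concern.** A sensitivity analysis for missing biopsies is useful if a difference from the completer result says something about the missing data. Here the missing values in every arm come from one regression line fitted to all arms together. If there is a treatment effect, that line lies between the arms, so filled-in placebo values are too high and filled-in resveratrol values too low for participants who would have followed their own arm. The estimate then moves although nothing is wrong with the completers.

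This is the only specified State 3 analysis that brings back randomised participants without a second biopsy. A reader who saw a smaller imputed effect could not separate harm from dropout from the rule's own shrinkage, and would have no specified counterpart to the primary contrast.

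**Working it through.** **Inputs from section 9.2.** 20 randomised and 18 completers per arm (10% missing), State 3 SD 40 and mean 120, baseline-to-final correlation 0.7, detectable differences 0.69 SD (contrast) and 0.81 SD (pairs). In units these are 0.69 × 40 = 27.6 and 0.81 × 40 = 32.4, or 23% and 27% of 120, in line with the plan's 25% and 30%.

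**The plan's power figure.** The plan says that "18 completers in each of the three groups has 80% power to detect a difference of 0.69 standard deviations in this contrast". The change-score SD is √(2 × 0.3) = 0.775 SD and the contrast standard error is 0.775 × √(1/18 + 1/36) = 0.224 SD. Power at 0.69 SD is then 85.0% (34 df), 85.7% (51 df) or 87.0% (normal), so 80% is not reproduced; 80% power falls at 0.63 to 0.65 SD. The discrepancy is conservative and does not affect this point.

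**Assumptions not in the documents.** Missing rates other than 10%; BMI and sex unrelated to outcome; the strength of baseline-related dropout; equal dose effects unless stated.

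**Random dropout, own-arm condition.** The expected filled-in arm mean is (1 − f)μ + f × P, where μ is the arm's true mean effect and P is the mean over all observed participants. With equal f, P cancels and the difference is (1 − f)d:

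- 10% per arm: 27.6 × 0.9 = 24.8; 32.4 × 0.9 = 29.2. The shortfalls are 0.07 and 0.08 SD.
- 25% per arm: 27.6 × 0.75 = 20.7; 32.4 × 0.75 = 24.3.
- 30/10/10% (A/B/C), d = 32.4: P = 36 × 32.4/50 = 23.3. A becomes 0.3 × 23.3 = 7.0, B becomes 29.16 + 2.33 = 31.5, and the difference is 24.5.

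Simulated B − A (4,000 runs; multiple imputation with arm, 20 imputations):

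| True effect, missing | Completers | Plan | Multiple imputation with arm |
|---|---|---|---|
| 27.6, 10% | 27.6 | 24.9 | 27.7 |
| 27.6, 25% | 27.7 | 20.7 | 27.6 |
| 32.4, 10% | 32.5 | 29.2 | 32.5 |
| 32.4, 30/10/10% | 32.3 | 24.5 | 32.4 |

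For the primary contrast at 27.6 and 10% missing the three values are 27.6, 24.8 and 27.6.

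**Direction.** The shift is not always toward zero. Take dose effects of 6.9 and 32.4 with 0/15/15% missing. P = 17 × 39.3/54 = 12.37, so B − A becomes 0.85 × 6.9 + 0.15 × 12.37 = 7.7. The contrast still falls, from 19.65 to 18.6.

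**Baseline-related dropout, the case the rule is meant for.** 10% missing per arm, opposite directions in placebo and active, 8,000 runs, Monte Carlo error about 0.1. Strength is log-weight per baseline SD. Bias in B − A at 27.6, for the two directions:

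| Strength | Completers | Plan |
|---|---|---|
| 0.5 | −1.27, +1.11 | −2.88, −2.94 |
| 1.0 | −2.19, +2.18 | −2.91, −3.03 |
| 1.5 | −2.80, +2.99 | −2.95, −3.12 |

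Completer bias hardly depends on the effect; the plan's bias grows with it. With no effect the plan's bias is −0.3 to +0.1. At strength 1.5 it is −0.97 and −0.90 for an effect of 8, against −3.05 and +3.00 for completers. Dividing completer bias by the plan's bias per unit effect (0.100, 0.108, 0.110) shows the rule is less biased than completers below effects of about 12, 20 and 27 units, and equal or worse above. Multiple imputation with arm stays within 0.25 at strength 1.5.

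**Tests.** Rejection, plan versus completer Welch: at 27.6, 70.5% versus 72.3% (10% missing) and 60.7% versus 63.7% (25%); at 32.4, 86.3% versus 87.4% and 75.3% versus 79.2%. Permutation type I error was 4.2% to 4.4%, and about 5.5% in a separate simulation.

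**The case against.** The bias depends on participants without a biopsy following their own arm. Seeking biopsies regardless of adherence points to a treatment-policy target, and people who stop may lose the benefit. With 10% missing per arm, an effect of 32.4 and all benefit lost, the true policy effect is 0.9 × 32.4 = 29.2. The plan gives 29.2, while completers and multiple imputation with arm give 32.4. With half lost the truth is 30.8. This stands, but the plan does not state that assumption, and the agreement needs equal missingness: at 30/10/10% the full-loss truth is still 29.2 and the plan gives 24.5.

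The paragraph claims only to correct baseline imbalance, and leaving treatment out is a deliberate choice that holds the test's level under the null. That also stands, and the rule does its job when the effect is nil or small. It does not do so at the effect the trial is sized for.

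The comparison at 27.6 is close at the strongest dropout, where plan and completer biases differ by only about 0.15. At the recomputed 80%-power difference of 0.63 to 0.65 SD (25.2 to 26.0 units), the rule would be slightly less biased there. At the two weaker strengths the ordering does not change.

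At 10% missing the shift is small beside a completer half-width of 20.9. Finally, the contrast's point estimate is the average of B − A and C − A, so it could be derived from the filled data. What the plan lacks is a stated imputed estimate, test and interval for it.

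**Conclusion.** The concern holds. When resveratrol works and participants without a second biopsy would have followed their own arm, the specified analysis differs from completers even if dropout is random. The loss equals the missing fraction when missingness is equal across arms: about 2.8 of 27.6 units at the planned 10%, and 6.9 at an assumed 25%. With equal dose effects and unequal missingness the difference also shrinks; with very unequal doses and unequal missingness, the weaker dose's difference can move away from zero. Under the baseline-related dropout it targets, the rule's bias at 27.6 is about equal to or larger than that of completers at all three assumed strengths. The primary contrast has no specified imputed check.

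The consequence is limited. The main Satterthwaite completer estimates are unaffected, type I error is kept, and power falls by one to two percentage points at 10% missing. This is a change worth considering, not a threat to the primary result.

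**What to change.** Replace the single prediction with multiple imputation of 90-day State 3 from arm, baseline State 3, BMI and sex, combined by Rubin's rules, with the number of imputations and the seed stated. Apply it first to the contrast of the mean of B and C with A, then to the three pairs. State the assumption that participants with a missing biopsy follow their own arm given baseline.

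Do not simply add arm to the single prediction. That removes the shrinkage, but type I error rises to 6.4% at 10% missing (7.5% in a separate simulation) and 12.0% at 25%. Multiple imputation with arm gave 4.3% to 5.1%.

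Optionally, add a delta-shift in the active arms running from no loss to full loss of benefit, because imputation with arm overstates a treatment-policy effect if dropouts lose benefit. If the present rule is kept as an extra scenario, label it as conservative and state its assumption.

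The cost is SAP wording and a little analysis work. At 10% missing the mean pairwise half-width is 21.1, against 20.9 for completers and 19.2 for a Welch interval on the single fill-in.

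### No planned analysis shows how far the primary State 3 contrast depends on 90-day biopsies still missing because of treatment

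*Combined protocol and SAP*

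**What the plan says.** The primary test in Section 9.1 asks whether "the unweighted average of the target population means B and C is the same as that of A", where A is placebo and B and C are the two resveratrol doses. As the dependent variable, "we will use the difference between the post-test value (90 days) and baseline".

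Section 9.3 calls its primary population intent-to-treat but defines it as "synonymous to those getting baseline and three-month biopsies", regardless of adherence. For State 3 that is a complete-case analysis.

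Section 9.2 plans two missing-data analyses:

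- **Baseline imbalance.** Missing final State 3 is predicted from baseline BMI, baseline State 3 and gender, without treatment, and each pair of arms is re-tested by permutation. The plan says that this does not deal with missingness arising from treatment, and gives headache leading to withdrawal as its example.
- **Withdrawals.** There are four steps. The first is to seek a follow-up biopsy from everyone, on study product or not. The second is to ask for reasons. The third is to "compare the withdrawal rates for the three treatment groups via an exact chi-square analysis". The fourth reads: "we shall compare the BMI trajectories for withdrawals vs. non withdrawals, stratified for treatment as a surrogate". BMI at months 1 and 2 would be used, as an indication of how the participant is doing.

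**The concern.** The plan identifies treatment-related loss of the second biopsy as the case that its imputation cannot handle, and offers the withdrawal block for it. The first two steps of that block are sound conduct. The two analyses that follow look at something other than the endpoint. Withdrawal rates say how many left, and BMI over one or two months says something about body weight. The documents give no link between short-term BMI and State 3 respiration.

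Such loss is foreseeable. Section 8 allows removal for toxicity related to resveratrol, and Section 7.1 withdraws participants who use prohibited interventions. If those without a second biopsy responded differently from completers, the complete-case contrast is shifted, and nothing planned shows by how much or whether the conclusion would survive.

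**Working it through.** **Inputs.**
- From Section 9.2: 20 randomised and 18 completers per arm, baseline to post-test correlation r = 0.7, State 3 mean about 120 and SD about 40.
- From Section 9.1: the contrast (B+C)/2 − A on change from baseline, two-sided 0.05, Satterthwaite.
- The plan states no dropout rate. 18 of 20 implies 2 missing per arm (10%), or 6 in all.
- Assumed here: equal variances, the observed contrasts, the uneven missingness, the withdrawal rates, and the complete-case standard error (SE) throughout, so the tipping values are approximate.

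**Plan's figure.** The plan says that "18 completers in each of the three groups has 80% power to detect a difference of 0.69 standard deviations".
- SD of change = √(2(1 − 0.7)) = 0.775 SD.
- SE = 0.775 × √(1/18 + 1/36) = 0.224 SD, df = 34.
- Power at 0.69 SD is 85.0%, against 80% stated. The stated value is conservative and the difference does not bear on this point.

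**Smallest significant contrast.** 2.032 × 0.2236 = 0.454 SD, or about 18 units.

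**Shift from missing biopsies.** If a fraction f of each active arm is missing and those participants did δ worse than completers in their arm, the contrast falls by f × δ. With f = 2/20 and δ = 1 SD, the fall is 0.10 SD = 4 units.

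**Tipping point, planned missingness (2/2/2), shift in active arms only.** δ = (observed − 0.454)/0.10.
- Observed 0.69 SD: 0.236/0.10 = 2.4 SD (94 units, about 79% of the mean of 120).
- Observed 0.50 SD (assumed): 0.0456/0.10 = 0.46 SD (18 units).
- If missing placebo participants also did better by the same amount, the divisor is 0.20 and the values halve, to 1.2 and 0.23 SD.

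**Tipping point, none missing on placebo and 4 of 20 in each active arm (assumed).**
- SE = 0.775 × √(1/20 + ¼(1/16 + 1/16)) = 0.221 SD, df about 40, smallest significant contrast 2.021 × 0.2208 = 0.446 SD.
- δ = (observed − 0.446)/0.20, which is 1.2 SD at 0.69 and 0.27 SD (11 units) at 0.50.

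**What the rate test can show.** The exact chi-square was fully enumerated with 20 per arm and assumed true withdrawal on placebo and the two doses:

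| True withdrawal | Power |
|---|---|
| 5/15/15% | 8.7% |
| 5/20/20% | 18.4% |
| 5/25/25% | 32.5% |

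Observed withdrawals of 0, 4 and 4 give p = 0.11. Withdrawals of 2, 2 and 2 give p = 1.00 whatever the missing State 3 values are.

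**What the BMI comparison can show.** Six withdrawals stratified by treatment is about 2 per arm. Anyone leaving before day 30 has no follow-up BMI. The schedule in Section 6.1 has weight at days 30 and 60, but the visit lists in Section 6.2.4 omit it.

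**The case against.** The plan deserves credit on several counts.

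- **Retrieval.** Sections 9.2 and 9.3 commit to seeking the second biopsy whatever the adherence, and Section 8 continues follow-up, with permission, after discontinuation. Retrieved biopsies are real State 3 values and are the main protection. Withdrawal is therefore not the same as a missing biopsy. This stands, but it says nothing about biopsies that remain missing.
- **State 3 is re-tested under imputation.** It is. Leaving treatment out of the prediction would tend to pull a real effect toward the null. But it is one fixed assumption, it covers pairs of arms rather than the primary contrast, and the plan itself excludes treatment-caused withdrawal from it.
- **Last observation carried forward.** That sentence follows the one on secondary repeated measures. Applied to State 3 it would set the change to zero, again a single assumption.
- **The plan does not oversell the two comparisons.** A reader might infer that it offers similar rates or similar BMI curves as proof of safety from bias. The text does not support that. It says that the events may not be measurable, that similar rates need not resolve the question, and that BMI is only a surrogate.

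A reader might also infer that the primary result is likely to be overturned by dropout. The plan's own figures do not support that either: at planned missingness and an observed 0.69 SD, the shortfall needed is about 2.4 SD.

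**Conclusion.** The point holds as a gap in the planned sensitivity analyses. It is not evidence that the primary result will be biased. The primary analysis is complete-case, the plan sets treatment-related missingness outside its imputation, and the withdrawal block returns no State 3 estimate.

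The size depends on the result. With 2 of 20 missing per arm, each 1 SD shortfall among missing active participants costs 0.10 SD. That is harmless if the observed contrast is near 0.69 SD and decisive if it is near 0.50 SD. Heavier and uneven loss (0/4/4, assumed) brings the tipping points down to about 1.2 and 0.27 SD. These values rest on r = 0.7, equal variances, the complete-case SE and the assumed observed contrasts. The low power of the rate test is supporting detail, since the plan already declines to treat equal rates as decisive.

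**What to change.** Add to Section 9.2 a delta-adjusted tipping-point analysis of the primary (B+C)/2 versus A contrast in all randomised participants with a baseline biopsy:

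1. Multiply impute missing 90-day State 3 from baseline State 3, baseline BMI, sex and treatment arm.
2. Shift the imputed values by separate amounts in the active and placebo arms.
3. Extend the shifts until the conclusion changes, or to a limit stated in advance as implausible. A grid ending at 1 SD would stop short of the tipping point for an observed 0.69 SD in both active-only scenarios above.
4. Report the tipping values in SD and in State 3 units.

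Keep biopsy retrieval and the reasons questionnaire. Report withdrawal counts, reasons and BMI by arm as description only.

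No new data or visits are needed. The cost is a paragraph, a short program and a delta range fixed before unblinded analysis.
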